6.2.7 Hospitalizations, Emergency Department Visits and Observational Unit Stays

The number and percent of patients who were admitted to hospital or not admitted to the hospital following their initial evaluation in the ED will be

[Redacted]

tabulated in a frequency table by the pre-period and post-period for the FAS population. Patients' care pathways, including time spent in each setting of care (ED, observation unit, initial hospitalization, and ICU), will be summarized with descriptive statistics. The number and percentage of patients will be reported for treatment with dalbavancin, alive or dead at discharge, and discharge disposition location. All of the aforementioned variables will be reflected in listings.

6.2.8 Clinical Assessments

Vital signs including temperature (°C), method of collection of temperature, heart rate (beats per minute), respiratory rate (breaths per minute), systolic BP (mmHg), diastolic BP (mmHg), height (cm), weight (kg) and BMI (kg/m²) will be summarized at baseline and the 48-72 hours after enrollment follow-up visit (post-period only).

Height is collected in both inches (in) and centimeters (cm) and will be reported in centimeters in the analysis. If height is reported in inches then it will be converted as follows:

$$\text{Height (cm)} = \text{reported value (inches)} * 2.54$$

Weight is collected in both pounds (lbs) and kilograms (kg) and will be reported in kilograms in the analysis. If weight is reported in pounds then it will be converted as follows:

$$\text{Weight (kg)} = \text{reported value (lbs)} * 0.4536$$

Temperature is collected in both degrees Celsius and Fahrenheit and will be reported in degrees Celsius in the analysis. If temperature is reported in degrees Fahrenheit then it will be converted as follows:

$$\text{Temperature (°C)} = (\text{reported value (°F)} - 32) / 1.8$$

Clinical assessments will be summarized with descriptive statistics for baseline and the 48-72 hour visit (post-period only) by the pre-period and post-period for the FAS population. Values will be summarized in tables and listings, and in listings, reported with the visit date and change from baseline for follow-up values.

6.2.9 Antibiotic Treatments and Concomitant Medications

Concomitant medications taken three months prior to study start will be coded using the WHODRUG dictionary, Version B2 201609 or later, and the number and percentage of patients will be summarized in tables. Antibiotic usage during the study will also be coded using the WHODRUG dictionary, Version B2 201609 or later, and summarized in tables. The most current WHODRUG

dictionary will be used at the time of analysis. These prior non-antibiotic medications used for chronic conditions will be reported in listings, including the medication name (coded), reason for prescription, route, and start date and end date. All medications will be summarized using descriptive statistics by the pre-period and post-period for the FAS population. For post-period patients, discharge to complete care in an outpatient setting on the same day Dalvance was provided and reasons for not being discharged to an outpatient setting will be summarized by patient counts and percentages.

6.2.10 Safety Assessments

The reporting period for adverse events (AEs) begins from the time of the signing of the Patient Authorization throughout the patient's enrollment in the study. AE information will be collected in an ongoing fashion through patient reporting AEs to their healthcare provider.

All AEs will be coded and summarized by the pre-period and post-period for the FAS population by system organ class and preferred term based on the MedDRA coding dictionary Version 20.0 or later; the most current MedDRA coding dictionary will be used at the time of analysis. AEs will be summarized by relationship to treatment as yes, there is evidence to suggest a causal relationship between the study drug (any antibiotic given for ABSSSI from enrollment, including the pre-period or post-period) and adverse event, and no, there is no evidence to suggest a causal relationship between the study drug and adverse event. For severity, the most severe case of an AE by a patient will be reported, with order of most severity as: Severe>Moderate>Mild.

A listing of adverse events will also be given for each patient and will include the reported term, seriousness, severity, relationship to treatment, action taken with medication, event outcome and date for each event reported.

6.2.11 Laboratory and Microbiology

All laboratory and microbiological assessments will be summarized for baseline and follow-up visits in tables with descriptive statistics by the pre-period and post-period for the FAS population. Laboratory results will be reported for the scheduled baseline and 42-78 hour visits, with the latter laboratory results for post-period patients only. The first microbiology result for each patient at baseline and follow-up, respectively, will be summarized for each time period. Where more than one unit is collected within analysis, values will be converted to a common unit and displayed for analysis. Laboratory conversions to standard international units are reported in the table below:

Laboratory Unit	Standard International Unit	Factor
------------------------	------------------------------------	---------------

Sodium mEq/L	Sodium mmol/L	x1
Potassium mEq/L	Potassium mmol/L	x1
Bicarbonate mEq/L	Bicarbonate mmol/L	X1

A listing of laboratory and microbiological assessments will also be given for each patient and will include the time period the assessment was taken (e.g., initial care, follow-up), date of assessment, laboratory test, reported laboratory value, reported laboratory unit, specimen type, method of collection, if any isolated were grown from the specimen, the organism grown, if this organism was tested for susceptibility, what antibiotics were used for susceptibility, the level of susceptibility (sensitive, resistant, intermediate, indeterminate) and the minimum inhibitory concentration (MIC) with corresponding unit.

6.2.12 Healthcare Costs

Total costs of care for each study patient over the 44-day period of interest will be estimated by multiplying estimates of utilization of healthcare services collected during the conduct of this study by corresponding unit costs. Unit costs will include: cost of day in hospital, cost of day in ICU, emergency department visit, healthcare visits, surgical procedures, imaging tests, catheter placement (PICC line/central line) and microbial culture. Further detail can be found in Section 4.6 of this document.

Summary statistics for total costs of care will be estimated for the pre-period and post-period for the FAS population.

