2.2.2 Post-period

During the post-period, all enrolled subjects will receive treatment for ABSSSI with dalbavancin at each participating site. Dalbavancin will be administered as a single IV dose of 1500 mg over 30 minutes (1125 mg over 30 minutes if CrCl <30 mL/min, for those not on regularly scheduled dialysis).¹² Dalbavancin will be provided to sites by study sponsor.

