5.1 Cost

Cost data will not be collected in the study. As these data often vary by site and insurer, representative unit cost estimates for each healthcare service/medication identified during the collection of outcome measures will be identified. Total costs of care for each study subject will then be estimated by multiplying utilization of healthcare services collected via the CRF by the corresponding unit costs; mean/median total costs of care during the pre- and post-periods will then be estimated and compared. The approach to the pre-post comparison and unit costs will be defined in the SAP.

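### The SAP's unit-cost list names no medication and no observation time, although the protocol promises medication unit costs; if the list is complete, total cost of care omits antibiotics in both periods

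*SAP*

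**What the plan says.** Protocol 5.1 (Cost) collects no cost data. It says that "representative unit cost estimates for each healthcare service/medication identified during the collection of outcome measures will be identified", and that total cost per subject comes from "multiplying utilization of healthcare services collected via the CRF by the corresponding unit costs". It hands the detail on: "The approach to the pre-post comparison and unit costs will be defined in the SAP".

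SAP 6.2.12 (Healthcare Costs) forms the 44-day total by "multiplying estimates of utilization of healthcare services collected during the conduct of this study by corresponding unit costs". Its list runs: "Unit costs will include: cost of day in hospital, cost of day in ICU, emergency department visit, healthcare visits, surgical procedures, imaging tests", followed by "catheter placement (PICC line/central line) and microbial culture". It then adds: "Further detail can be found in Section 4.6 of this document". The visible SAP section headings go from 4.4 to 4.7, so Section 4.6 cannot be read.

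Other relevant places:
- SAP 5.0, which records departures from the protocol's analyses, says nothing about costs.
- SAP 6.1.1 admits pre-period patients to the full analysis set (FAS) only if they received at least one antibiotic dose, and post-period patients only if they received at least one dalbavancin dose.
- Protocol 2.2.2 states: "Dalbavancin will be provided to sites by study sponsor".
- SAP 6.2.9 has antibiotic use during the study coded and tabulated.

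**The concern.** The list is specific enough to name imaging and cultures, yet it omits the drug that forms the second component of the pathway. It also omits the antibiotics that this drug replaces. The protocol's wording covers medication explicitly, so a reader who follows the SAP list would produce a total that the protocol does not describe, with no declared reason.

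The output is a total cost of care by period (SAP Table 27), and protocol 1.2 gives economic benefit as part of the study's purpose. A total that counts avoided bed-days but not the drugs used in either period is not a total, and a reader of Table 27 could not tell what had been left out.

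Observation time raises a related problem. Under SAP Appendix B, a patient counts as admitted only if the discharge destination from the initial episode is the hospital. Release from the ED to observation is a separate route in the ED length-of-stay definition. Care moved from admission to observation could therefore carry no cost under the listed items.

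**Working it through.** The documents state no unit price, total cost or cost difference, so there is no cost figure to reproduce. The check is a comparison of texts, followed by a break-even calculation for scale.

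**Comparison of texts**

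| Item | Protocol 5.1 | SAP 6.2.12 list | Data available |
|---|---|---|---|
| Hospital and ICU days | covered as services | named | yes |
| ED and other visits, surgery, imaging, lines, cultures | covered as services | named | yes |
| Antibiotics and other medication | covered by name | not named | antibiotic use: SAP 6.2.9, Table 9, Listing 6; antibiotic days: Appendix B |
| Observation time | not named separately | not named | observation hours: SAP 6.2.5, 6.2.7, Appendix B |

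The conflict over medication is visible in the text, and SAP 5.0 does not declare it. The observation gap is an omission from the list, not a direct contradiction of the protocol.

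**What would be left out if the list is complete**

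Let D be the mean antibiotic cost per post-period FAS patient. It includes dalbavancin for every patient, by the FAS definition. Let U be the mean antibiotic cost per pre-period FAS patient; all of these patients also received an antibiotic.

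Error in the post-minus-pre cost difference = −(D − U).

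The error is the net difference, not the dalbavancin price. The documents give neither D nor U, so neither its sign nor its size can be computed.

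**Scale**

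Inputs: planning admission rates of 38% (pre) and 23% (post), from protocol 5.3 and SAP 6.1.2. The length of an admission, L days, is an assumption and is taken as equal in the two periods.

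Hospital-day unit costs saved per patient = (0.38 − 0.23) × L = 0.15 × L.

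| Assumed L (days) | 0.15 × L |
|---|---|
| 2 | 0.30 |
| 3 | 0.45 |
| 4 | 0.60 |
| 5 | 0.75 |
| 6 | 0.90 |

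If D − U exceeded 0.15 × L hospital-day unit costs, leaving drugs out would hide a net drug cost larger than the saving from avoided admissions alone. This is a threshold, not an estimate of D − U.

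**Bundling**

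The documents do not say whether the hospital-day cost already contains inpatient drugs. If it does, antibiotics given to admitted patients are partly costed, while a dose given in the ED may not be. The omitted amount would then differ from D − U as defined above.

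**The case against.** The strongest reply is that the list may not be the whole plan. It is introduced by wording that need not be exhaustive, and it refers to a section that is absent from the public text. The SAP abbreviation list also defines a cost-to-charge ratio that appears nowhere in the visible text, which suggests that some costing method sits in the part we cannot see. This stands. The absence of Section 4.6 is not a fault in the plan, and the point has to be conditional on the list being complete. What remains is that the visible list does not match the protocol.

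A second reply is that the protocol's own total-cost formula refers to healthcare services only. That is true, but the sentence before it covers medication explicitly.

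A reader might also infer stronger conclusions, which the documents do not support:
- *Dalbavancin is counted as free because the sponsor supplies it.* Neither document says so. Costs come from external representative prices, so who paid for the drug does not set its price.
- *The bias runs in one direction.* Usual-care antibiotics are missing from the list too, and no prices are given.
- *The listed items would show a saving whatever happens.* The result depends on observed use. The post-period adds a scheduled visit at 48–72 hours (protocol 3.2.1), and visits are a costed item.

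Part of the omission may already be covered. Infusion-center and home-health visits count as outpatient visits, so some administration cost may be captured. Observation longer than one day enters the second length-of-stay method for hospital days, although the visible text does not say which method feeds the costs.

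Finally, cost is not a listed primary or secondary objective, and the SAP plans only summary statistics for it. This limits the weight of the point.

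**Conclusion.** The point holds in a limited, conditional form. There is an undeclared conflict between protocol 5.1 and the unit-cost list in SAP 6.2.12, and the list also leaves out observation time. If the list is followed as written, the total is incomplete in both periods, and the pre-post difference is off by the net antibiotic cost, apart from any drugs bundled into the hospital-day cost.

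The range of 0.30 to 0.90 hospital-day unit costs rests on the planning admission rates and on an assumed stay of 2 to 6 days. It shows how large a net drug cost would have to be to matter, not how large it is. Whether the pathway would look better or worse than it should cannot be settled from these documents.

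The consequence is confined to the descriptive cost summary in Table 27. The conflict should be resolved before that table is produced.

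**What to change.** 1. In SAP 6.2.12, add representative unit prices for all antibiotics given from enrolment to day 44 in both periods. Include dalbavancin at such a price regardless of sponsor supply.
2. State whether the hospital-day cost already contains inpatient drugs. If it does, do not cost those drugs a second time.
3. Add a unit cost for observation time, and say which length-of-stay method feeds the hospital-day cost, so that prolonged observation is not counted twice.
4. Make SAP 6.2.12, SAP 4.6 and protocol 5.1 agree. If Section 4.6 already contains these items, correcting the 6.2.12 list is enough. If medication costs are left out on purpose, declare this in SAP 5.0 and label Table 27 as excluding drug costs.

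The work is a few extra unit prices and some sentences, because antibiotic use and observation hours are already recorded. The drawback for the sponsor is that the cost difference may become less favourable to the pathway.

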7.0 List of Potential Tables/Listings/Figures

Table shells are included in the file 055123_ADVANCE_SAP_Table Shells_v 1.0_20181204.docx.

§ Denotes output that can be produced at interim analysis. f Denotes the minimum output necessary to support sample size confirmation. * Denotes output to be produced only for the sample size confirmation described in the protocol.

Table 1 Disposition of Study Patients by Site and All Patients: Enrolled Set§f
Table 2 Study Site Characteristics §
Table 3.1 Patient Demographics at Baseline by All Patients: Enrolled Set§
Table 3.2 Patient Demographics at Baseline by Site 10X: Full Analysis Set
Table 4 Comorbid Conditions Reported at Baseline: Full Analysis Set§
Table 5 Healthcare Resource Utilization at Previous 3 Months: Full Analysis Set§
Table 6 Infection characteristics and clinical characteristics during the initial assessment in the ED: Full Analysis Set§
Table 7.1 Care Pathways of Patients Following Initial Episode of Care: Full Analysis Set§
Table 9 Use of Antibiotics by Patients During the Study: Full Analysis Set§
Table 10 Primary Outcome: Hospital Admission Rate at Initial Episode of Care Full Analysis Set§f
Table 11 Primary Outcome: Primary Outcome: Hospital Admission Rate at Initial Episode of Care Multivariate Analysis Full Analysis Set§f
Table 12.1 Secondary Outcome: Total LOS during Initial Care and Follow-up: Full Analysis Set§f
Table 12.XX Secondary Outcome: Total LOS during Initial Care and Follow-up: Full Analysis Set: Site XXX§f
Table 13.1 Secondary Outcomes by All Patients: Full Analysis Set§
Table 13.2 Secondary Outcomes: Infection-related outpatient healthcare visits by Site 101: Full Analysis Set
Table 13.XX Secondary Outcomes: Infection-related outpatient healthcare visits by Site 10X: Full Analysis Set
Table 14 Secondary Outcome: Serious Adverse Events by SOC and PT: Full Analysis Set§
Table 15 Secondary Outcomes: Patient Satisfaction with Care: Full Analysis Set §
Table 16 Secondary Outcomes: Patient Work and Productivity Loss: Full Analysis Set§
Table 17 Secondary Outcomes: Patient Health-Related Quality of Life (SF-12): Full Analysis Set
Table 18 Other Outcomes: Full Analysis Set§
Table 19 Adverse Events- Overall Summary: Full Analysis Set§
Table 20 All Adverse Events by SOC and PT: Full Analysis Set§
Table 21 Adverse Events with Possible Causal Relationship to Study Drug by SOC and PT: Full Analysis Set§
Table 22 Adverse Events Leading to Study Discontinuation by SOC and PT: Full Analysis Set§
Table 23 Adverse Events Leading to Death by SOC and PT: Full Analysis Set§
Table 24 Laboratory Values: Full Analysis Set§
Table 25 Microbial Assessments: Full Analysis Set§
Table 26 Vital Signs: Full Analysis Set§
Table 27 Summary of Cost Analyses over 44 Day Period: Full Analysis Set
Table 28 Sample Size Confirmation f*
Table 29 Sample Size Confirmation with Variations of Power and Statistical Significance *
Table 30 Secondary Outcome: ED LOS during Initial Care and Follow-up: Full Analysis Set*

Figure 1 Box plot of all-cause hospitalization time during initial care and follow-up by period: Full Analysis Set

Figure 2 Box plot of infection-related hospitalization time during initial care and follow-up by period: Full Analysis Set

Listing 1 Patient Disposition: Enrolled Set§

Listing 3 Patient Demographics at Baseline: Enrolled Set§

Listing 4.1 Medical History at Baseline Visit: Enrolled Set, Part 1§

Listing 4.2 Medical History at Baseline Visit: Enrolled Set, Part 2§

Listing 4.3 Medical History at Baseline Visit: Enrolled Set, Part 3§

Listing 4.4 Medical History at Baseline Visit: Enrolled Set, Part 4§

Listing 5 Infection Characteristics at Baseline: Enrolled Set§

Listing 6 Antibiotic Usage: Enrolled Set §

Listing 7 Prior Non-Antibiotic Usage for Chronic Conditions Reported at Baseline: Enrolled Set§

Listing 8 Hospitalization, ED and Observation Unit Visits: Enrolled Set §

Listing 9 Hospitalization Length of Stay: Enrolled Set §

Listing 10 Other Healthcare Visits: Enrolled Set§

Listing 11 SF-12 Questionnaire at Baseline and Day 14: Enrolled Set

Listing 12 Patient Satisfaction Survey at Day 14: Enrolled Set

Listing 13 WPAI at Day 14: Enrolled Set

Listing 14 Surgical Interventions and Procedures: Enrolled Set§

Listing 15 Adverse Events: Enrolled Set§

[figure not shown]
Listing 16 Laboratory Results: Enrolled Set§

Listing 17 Microbial Assessments: Enrolled Set§

Listing 18 Vital Signs and Physical Examination at Follow-up: Enrolled Set§

Appendix B: Derived Variables

Analysis Section (Visit)	Variable (Units)	Definition
General (Baseline)	Enrollment date	Informed consent date
General (Baseline)	Baseline date	Initial ED admission date
General (Initial Care)	Initial care indicator	If enrollment date \leq date \leq enrollment date + 13 days then = Yes Else = No
General (Follow-up)	Follow-up indicator	If enrollment date + 14 \leq date \leq enrollment date + 43 days then = Yes Else = No
Demographics (Baseline)	Age (years)	Round down to nearest integer((Initial ED admission date - date of birth + 1)/365.25), when both dates are available.
Demographics (Baseline)	BMI	weight (kg)/ [height(m)] ² Where necessary, height and weight will be converted to proper units.
Infection Characteristics (Baseline)	CCI	Will be scored as described in Appendix C. Includes variables for raw score and 10 year survival probability.
Infection Characteristics (Baseline)	Fever	If temperature > 38 ° C then =Yes Else =No
Infection Characteristics (Baseline)	Morbid Obesity	If baseline BMI \geq 40 then =Yes Else =No
Infection Characteristics (Baseline)	SIRS Criteria Met	SIRS criteria include abnormalities in temperature, heart rate, respiration, and white blood cell count. Specifically included are: 
 Fever of more than > 38.0°C or hypothermia with temperature < 36.0°C

[figure not shown]
[figure not shown]
Analysis Section (Visit)	Variable (Units)	Definition
		
 • Tachycardia with heart rate > 90 beats/minute or • Tachypnea with respiratory rate of > 20 breaths/minute or PaCO₂ of less than 32mmHg • Abnormal white blood cell count: leukocytosis >12,000/microliter, leucopenia <4,000/microliter, or >10% immature cells (bands).^{3,4} 
If 2 or more criteria present = Yes Else = No

Antibiotic Medications (Initial Care and Follow-up)	Days Received Antibiotic Medication	
Σ (Medication end date – Medication start date +1), when both dates are available. If dates overlap (e.g., end date and next start date are identical) then subtract 1 from summation for each occurrence.

Primary Outcome	Hospital Admission At Initial Episode of Care	
If discharge destination from the initial episode of care = Hospital and the reported hospitalization where discharge date = hospital date is infection-related then = Yes, Else = No

Secondary Outcomes (All visits)	Hospitalization LOS (days)	
For all-cause: Σ (Hospitalization end date – Hospitalization start date +1), when both dates are available. If ongoing at end of study or discontinuation date, use study completion date or discontinuation date as end date. For outcomes, LOS will be computed two ways: only in-patient hospitalizations visits and inpatient hospitalizations visits with prolonged observation

[figure not shown]
Analysis Section (Visit)	Variable (Units)	Definition
		
status (e.g., time in observation status exceeds 1 day).
 
For infection-related: Subset all-cause hospitalization time for patients with infection-related hospitalization stays

Secondary Outcomes (End of Study Visit)	Completers Flag	
If "Did the patient complete the study?" = 1 on the end of study visit CRF page and date of study completion does not equal missing, then =Yes, Else = No
 
This flag will be used to repeat certain primary and secondary outcomes that could be influenced by early discontinuation (e.g., LOS)

Secondary and Other Outcomes (Initial episode of care)	ED LOS (hours) Observation Status LOS (hours)	
Impute with estimated time where applicable for partial times. if admission date = discharge date then LOS (hours) = discharge time - admission time
 
else LOS (hours) = sum all hours over stay, with a full day counting as 24 hours

Secondary Outcomes (Follow-up)	WPAI	Scores and coded variables will be derived as described in Appendix D.
Secondary Outcomes (Initial Care and Follow-up)	SF-12	SF-12 sub-scores and total scores will be compiled using the Health Outcomes Scoring Software 5.0 by QualityMetric Inc. Further detail can be found in Appendix E.
Adverse Events (Baseline, Initial Care and Follow-up)	Highest severity AE	Severity of most severe AE for the patient with order of severity: Severe>Moderate>Mild Patients who only have AEs reported with missing severity,

Analysis Section (Visit)	Variable (Units)	Definition
		highest severity AE will be reported as missing

[Redacted]

[Redacted]

[Redacted]

[Redacted]

[Redacted]

[Redacted]

[Redacted]

[Redacted]

[Redacted]

[Redacted]

[Redacted]

[Redacted]

[Redacted]

[Redacted]

[Redacted]

[Redacted]

[Redacted]

[Redacted]

[Redacted]

[Redacted]

[Redacted]

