2.2 Antibiotic treatment

2.2.1 Pre-period

During the pre-period each participating site will be required to initiate treatment for ABSSSI with “usual care,” defined as investigator’s choice of antibiotic therapy (e.g., vancomycin, linezolid, and daptomycin), to each study subject who meets all study selection criteria. It is expected that choice of usual care will be site or physician specific. Dosing of each antibiotic agent should follow recommended guidelines, demonstrated for antibiotic agents in, but not limited to, Table 1 below. All included subjects require Gram-positive antimicrobial coverage for a known or suspected infection caused by susceptible isolates of the following microorganisms: *Staphylococcus aureus* (including methicillin-susceptible and methicillin-resistant strains), *Streptococcus pyogenes*, *Streptococcus agalactiae*, *Streptococcus dysgalactiae*, *Streptococcus anginosus* group (including *S. anginosus*, *S. intermedius*, *S. constellatus*) and *Enterococcus faecalis* (vancomycin susceptible strains).

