2.2.3 Rationale of dose/regimen of antibiotic treatment

Usual care antibiotic therapy and dalbavancin will each be administered per relevant guidelines/manufacturer instructions (dosing provided in Table 1). Duration of treatment

with usual care will be left to the physician's discretion, as recommendations for several agents include a range (e.g., 10–14 days for linezolid).²⁴

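### The antibiotic-days derivation in SAP Appendix B is exact only for a one-day overlap: on its plain reading, two agents given together for k days are overcounted by k − 1 days

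*SAP*

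**What the plan says.** SAP Appendix B has a row for the number of days on antibiotics during initial care and follow-up. The base quantity is a sum over records of "Medication end date – Medication start date +1", used when both dates are available. The overlap rule is "If dates overlap (e.g., end date and next start date are identical) then subtract 1 from summation for each occurrence". Its only example is a one-day handover. What counts as an occurrence is not defined, and nothing is said about agents that run together for two or more days.

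The treatments differ in shape between periods. Protocol 2.2.1 makes usual care the investigator's "choice of antibiotic therapy (e.g., vancomycin, linezolid, and daptomycin", among others. Protocol 2.2.3 leaves its duration to the physician because "recommendations for several agents include a range (e.g., 10–14 days for linezolid". Protocol 2.2.2 gives the post-period regimen: "Dalbavancin will be administered as a single IV dose of 1500 mg over 30 minutes".

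On reporting, SAP 6.2.9 states: "Antibiotic usage during the study will also be coded using the WHODRUG dictionary, Version B2 201609 or later, and summarized in tables", by period for the full analysis set. Table 9 in SAP 7.0 is titled "Use of Antibiotics by Patients During the Study: Full Analysis Set". The visible text attaches no hypothesis test to antibiotic days.

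**The concern.** A count of days on antibiotics should count a calendar day once, however many agents were given on it. Summing over records counts a shared day once per agent, so the overlap rule has to remove every repeated day. A flat subtraction of 1 does that only when exactly one day is shared.

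At stake is the accuracy of a descriptive comparison of antibiotic use between periods. The periods are not equally exposed to the error: it needs two records that share at least two days, and a single-dose record cannot supply one of them. There is also a reproducibility issue. SAP 6.1.9 calls for double programming of output tables, and two competent programmers could obtain different values from this text.

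**Working it through.** The documents state no figure for antibiotic days, so there is none to reproduce. The check applies the Appendix B rule to simple date patterns and compares it with the number of distinct calendar dates covered.

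**Inputs from the documents.** The record sum and overlap rule (SAP Appendix B); multi-day usual care (Protocol 2.2.1 and 2.2.3); a single-dose post-period regimen, so start date = end date = 1 day (Protocol 2.2.2).

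**The SAP's own case.** Days 1–3, then days 3–10: 3 + 8 − 1 = 10. The true count is 10, so the rule is exact here.

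**General result for two agents.** With durations a and b sharing k days, the true count is a + b − k. The plain reading gives a + b − 1. The excess is (a + b − 1) − (a + b − k) = k − 1, which is 0 for k = 1, 1 for k = 2, 9 for k = 10 and 13 for k = 14.

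**Four readings of an occurrence:** (a) each overlapping pair of records; (b) each consecutive overlapping pair; (c) only where an end date equals the next start date; (d) each overlapping day in each pair.

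| Records | Plain sum | (a) | (b) | (c) | (d) | True |
|---|---|---|---|---|---|---|
| Days 1–3, then 3–10 | 11 | 10 | 10 | 10 | 10 | 10 |
| Two agents, both days 1–5 | 10 | 9 | 9 | 10 | 5 | 5 |
| Days 1–5 and 4–10 | 12 | 11 | 11 | 12 | 10 | 10 |
| Two agents, both days 1–10 | 20 | 19 | 19 | 20 | 10 | 10 |
| Two agents, both days 1–14 | 28 | 27 | 27 | 28 | 14 | 14 |
| Three agents, all days 1–10 | 30 | 27 | 28 | 30 | 0 | 10 |
| Three one-day agents, same date | 3 | 0 | 1 | 1 | 0 | 1 |

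For three agents on days 1–10 there are three pairs sharing 10 days each, so reading (d) gives 30 − 3 × 10 = 0. None of the four readings is right in every row. Errors run upwards in most failing cases, but downwards in some.

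**Single-dose records.** Dalbavancin alone gives 1 (true 1). With one other agent on day 1 only: 1 + 1 − 1 = 1 (true 1). With one other agent on days 1–10: 1 + 10 − 1 = 10 (true 10). A post-period subject is overcounted on the plain reading only if two other multi-day agents run together. Dalbavancin on day 1 plus two agents on days 1–10 sums to 21, giving 21 − 3 = 18 under (a) or 21 − 2 = 19 under (b), against a true 10.

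**Effect on a period mean.** If a share f of subjects has one two-agent overlap of k days, the mean rises by f × (k − 1). Neither f nor k is in the documents, so these values are assumptions across a wide range:

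- f = 5%, k = 2: 0.05 × 1 = 0.05 days
- f = 10%, k = 5: 0.10 × 4 = 0.4 days
- f = 20%, k = 10: 0.20 × 9 = 1.8 days
- f = 50%, k = 14: 0.50 × 13 = 6.5 days

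**The case against.** The strongest reply is that the text is ambiguous rather than wrong. An occurrence could mean each overlapping day, and for two agents that gives the right answer (5 + 5 − 5 = 5). This stands for two agents. It does not rescue the rule, because the same reading returns 0 for three agents on days 1–10.

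A second reply is that a switch from one agent to the next is the case the SAP had in mind, and it is handled correctly. This stands for a switch with a one-day overlap; only overlaps of two or more days are affected.

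A third reply concerns how far the error travels, and most of it stands. A reader might infer that usual care will appear to need more antibiotic days than it does, and that cost comparisons will then favour the pathway. The documents do not support either step:

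- No section says that concurrent agents are expected under usual care, how often they are used or for how long. Protocol 2.2.1 says only that the choice varies.
- Post-period subjects on two other multi-day agents would be inflated too, and some patterns are undercounted. The direction between periods is likely, not shown.
- Much of the contrast between single-dose and multi-day treatment is set by the design. An overcount in the pre-period would add to that gap, not create it.
- In SAP 6.2.12, "Unit costs will include: cost of day in hospital, cost of day in ICU, emergency department visit, healthcare visits, surgical procedures, imaging tests", followed by catheter placement and microbial culture. No antibiotic item appears. Protocol 5.1 does foresee unit costs for medications, and SAP 6.2.12 refers to a Section 4.6 that is not in the text available, so a link to cost is possible but unproven. If drugs were costed, two concurrent agents really would cost two agent-days per calendar day.
- The title of Table 9 does not mention days, and the table shells are in a separate file. Whether and how the variable is tabulated cannot be confirmed.

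**Conclusion.** The rule is wrong as written for any two antibiotics that overlap for two or more days, on its plain reading, by k − 1 days per such pair in a two-agent subject. None of the four readings examined gives the correct count in general. Any overcount would fall mainly on the pre-period, because a single-dose record can share at most one day with another record.

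The figures of 9 against 5 and 19 against 10 describe individual subjects with complete overlap; they are not estimates of bias in a period mean. The mean shift depends on the unknown share and length of concurrent use, and the range of 0.05 to 6.5 days rests entirely on assumed values. Net direction is therefore not established.

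The point is minor. The variable is not among the listed primary or secondary outcomes, its visible use is descriptive, and the primary outcome, its power and the visible unit-cost list do not depend on it.

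**What to change.** Replace the Appendix B formula with a count of distinct calendar dates on which at least one antibiotic was given, taking the union of the start-to-end intervals over records with both dates available. This needs no overlap correction and holds for any number of agents: 10 for two or three agents on days 1–10, 5 for two agents on days 1–5, and 1 for several one-day agents on the same date.

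If total drug exposure or drug cost is also wanted, define agent-days as a separate variable, using the record sum without subtraction, and label it as such. Distinct dates would understate drug cost where agents are combined.

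The cost is a short edit to one row of Appendix B and some reprogramming. The start and end dates that the present formula needs are sufficient, so no new data are required.
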